##### **6.1.2.1. Efficacy Analysis**

- Proportion of subjects with objectively documented new or progressive symptomatic VTE during dalteparin treatment.

The count and proportion will be summarized overall and by each age group, along with the two-sided exact 95% CI.

- Relationship between objective documented new or progressive symptomatic VTE assessed by investigators and the anti-Xa level during dalteparin treatment.

Logistic regression for new/progressive VTE assessed by investigators on anti-Xa level at end of dose adjustment and other prognostic factors (eg, age, baseline tumor status), will be performed. For each of the covariates, the odds ratio, and the corresponding 95% CI, will be displayed.

Subjects who experience at least one new or progressive VTE while on study will be counted as Yes.

- Time to event (first episode of recurrent VTE) during dalteparin treatment.

The time to event (first recurrent VTE) will be described by using the Kaplan-Meier method. In addition, the Cox Proportional Hazard Regression model will be employed to assess the hazard ratio of the event with prognostic factors.

See [Appendix 1](#) for a general description of censoring of time-to-event variables.

- Proportions of subjects with progression, regression, resolution and no change in the qualifying VTE (in comparison with the assessment at study entry) during dalteparin treatment.

The count and proportion will be summarized overall and by each age group, along with the two-sided exact 95% CI.

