10. Study drug exposure to be assessed during telephone contacts.

11. Study drug will be dispensed to subjects according to their dosing requirements. Cancer patients will be dispensed study drug for the entire 3 months, whereas non-cancer patients will be dispensed study drug for the appropriate treatment period for them according to the ACCP Guidelines of 6 weeks to 3 months. Non-cancer patients will, however, be required to complete all remaining study visits, but no anti-Xa or anti-IIa plasma samples will be required once the non-cancer patients stop study drug.
12. During the Dose Adjustment Phase and Follow-Up Phase, if a plasma sample for anti-Xa is drawn outside the 4 hour (+/- 1 hour) window, the plasma sample for anti-Xa must be re-drawn the next day within the correct window and sent to the Local Lab and Central Lab. If this occurs, an Unscheduled Visit must be conducted to redraw the anti-Xa plasma samples. The actual dosing time prior to the repeat plasma sample draw and the actual time of the repeat sample draw must be recorded in the CRF.
13. Unscheduled Events are bleeding or VTE events that require an Unscheduled Event visit. Unscheduled visits are conducted for any other reason.
14. Urine collection for creatinine to be conducted if applicable, per institutional standards

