## 5. INVESTIGATIONAL PLAN

### 5.1. Overall Study Design and Plan – Description

The study is a 3-month prospective, multicenter, open-label cohort study in North America and Europe to determine twice daily dosing recommendations of dalteparin as a function of age in order to achieve Anti-Xa levels of 0.5 to 1.0 IU/mL at 4 hour ( $\pm$  1 hour) post-dose in children with or without various cancers and requiring anticoagulation for the treatment and secondary prophylaxis of VTE. The study is divided into 3 phases: 1) Dose Adjustment Phase of up to 7 days; 2) PD Phase; and 3) Follow-Up Phase, to complete up to 90 days of treatment for cancer patients and treatment of non-cancer patients should be aligned with the 2012 ACCP Guidelines which suggest a total duration of anticoagulation treatment of between 6 weeks and 3 months rather than shorter or longer durations (Grade 2C), following completion of the PD Phase. Non-cancer patients will be required to remain in the study, however, for the full 3 months to complete all remaining study visits, regardless of dalteparin treatment duration. For non-cancer patients who stop dalteparin treatment prior to 3 months, Anti-Xa and Anti-IIa plasma sampling will not be required after study medication discontinuation.

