### **5.3. Definition of End of Study and Early Discontinuation**

End of study (EOS) is defined as Day 90 ( $\pm$  14 days) after study Baseline. Early Discontinuation from Study Drug: Early discontinuation from study drug treatment will be defined as less than 90 days of study treatment for cancer patients. For non-cancer patients, between 6 weeks and 3 months, rather than shorter or longer durations (Grade 2C), following completion of the PD Phase (2012 ACCP Guidelines) due to: 1) new or recurrent VTE; 2) bleeding necessitating permanent discontinuation of anticoagulant therapy; 3) unexpected permanent discontinuation of anticoagulant therapy; 4) AEs necessitating discontinuation of study drug; 5) withdrawal of consent to participate in the

trial, or 6) inability to achieve therapeutic range during Dose Adjustment Phase. Non-cancer patients will be required to remain in the study, however, for the full 3 months, regardless of dalteparin treatment duration.

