However, the first Anti-Xa level may be taken after the first, second or third dose per Investigator judgment. The next dalteparin dose will be adjusted if the target therapeutic range is not achieved. If the therapeutic range is not achieved, the dalteparin dose must be adjusted per protocol. All plasma samples should be drawn within the assigned window at each visit, however, if this is not possible, record the actual time the sample is drawn). Plasma samples drawn during the Dose-Adjustment Phase and Follow-Up Phase that deviate outside the  $4 \pm 1$  hr window cannot use the anti-Xa reference range, 0.5-1.0 IU/mL, and should be repeated the next day for both central and local labs. The actual dosing time prior to the repeat plasma sample draw and the actual time of the repeat sample draw must be recorded.

After dose adjustment, Anti-Xa levels should be re-measured after the first, second or third dose per Investigator judgment. Dosage can be adjusted a maximum of up to 6 times (up to Day 7) to achieve Anti-Xa therapeutic range. If the target range is not achieved within the 7 day period, the subject is withdrawn from the study.

The dose at which a therapeutic Anti-Xa level is achieved is then maintained as the therapeutic dose in subsequent phases of the study unless dose adjustment is necessary.

- Pharmacodynamic Phase (Following completion of Dose Adjustment Phase) Day 2 or 3 up to Day 14 [up to 7 days]: Subjects completing the Dose Adjustment Phase will enter into the PD Phase and continue daily dosing every 12 hours  $\pm 1$  hour of dalteparin sodium with the final maintenance therapeutic dose from the Dose Adjustment Phase (no less than 8 hours between doses). However, if a dose is not able to be delivered every 12 hours  $\pm 1$  hour, administer the dose (no less than 8 hours between doses) and record the actual dosing time. The plasma sample should be re-drawn, if possible, at the correct time point.
- Follow-up Phase (Visits 5, 6 and 7, following completion of Pharmacodynamic Phase): Dalteparin sodium will be administered subcutaneously every 12 hours  $\pm 1$  hour (no less than 8 hours between doses) during Visits 5, 6 and 7. However, if a dose is not able to be delivered every 12 hours  $\pm 1$  hour, administer the dose (no less than 8 hours between doses) and record the actual dosing time.

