## 9. ASSESSMENTS AND ENDPOINT DEFINITIONS

### 9.1. Endpoint Definitions

#### 9.1.1. VTE Endpoints

A suspected new or progressive symptomatic VTE, in the same anatomical region, should be documented with the same imaging method used at Screening/Baseline. Suspected new or progressive VTE in a different anatomical region should be documented utilizing institutional standards. These images should be collected and be included in the primary source records. Thrombus resolution of the qualifying event will be measured by repeat imaging at the EOS visit (using the same modality as that which was used to diagnosis the thrombosis prior to enrollment). If an image has been captured prior to the EOS and it demonstrates complete resolution of the qualifying VTE, then a repeat image does not need to be done again at day 90. For purposes of the study, the complete resolution image will be the “EOS” image for the index event.

In the assessment of a new or progressive symptomatic thrombus, the following general definitions will be utilized;

**Symptomatic New VTE:** Symptomatic VTE confirmed by at least one radiographic test. Asymptomatic VTE within a venous segment noted to be patent on a prior imaging study. Symptomatic will be defined as: New or progressive signs and symptoms as judged by the investigator including but not limited to:

- Objective swelling;
- Pain or tenderness;
- Pitting edema;
- Erythema or cyanosis.

**All New VTE:** All VTE confirmed by at least one radiographic test.

**Stable VTE:** Follow-up study demonstrating stable clot burden utilizing the same imaging modality as the Screening Visit.

**Regression of VTE:** Follow-up study demonstrating regressed clot burden utilizing the same imaging modality as the Screening Visit.

**Progression of VTE:** Progression of clot burden on a follow-up study in terms of severity of occlusion, or involvement of new venous segments at any time after the initial diagnosis.

In the assessment of a new or recurrent PE, the following general definitions will be utilized;

**New PE:** Symptomatic PE confirmed by presence of an intraluminal filling defect of the pulmonary artery on CT angiography and/or a mismatched defect on a nuclear V/Q scan. All new PE's will be considered to be a symptomatic event.

**Stable PE:** Follow-up study demonstrating stable clot burden utilizing the same imaging modality as the Screening Visit.

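### The qualifying-clot outcome is labelled as on-treatment, but a non-cancer child who finishes a short planned course can be classified from an image taken weeks off drug

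*SAP*

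**What the plan says.** SAP 6.1.2.1 lists as an efficacy result "Proportions of subjects with progression, regression, resolution and no change in the qualifying VTE (in comparison with the assessment at study entry) during dalteparin treatment". It is to be given overall and by age group, with an exact 95% confidence interval, in the PD population. Protocol 4 and 12.3.5 limit the endpoint to the same period.

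Protocol 9.1.1 names the image that supplies the answer: "Thrombus resolution of the qualifying event will be measured by repeat imaging at the EOS visit". After baseline, Table 1 schedules imaging only at Visit 7 (Days 75 to 104) and at an unscheduled event. Protocol 5.3 says "End of study (EOS) is defined as Day 90", with 14 days either side. An earlier image that shows complete resolution takes the place of the end-of-study image (protocol 9.1.1). Footnote 8 to Table 1 requires imaging when a new or recurrent VTE is suspected and otherwise leaves it to the investigator.

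Planned treatment length differs by group. Cancer patients are to be treated for 90 days. Non-cancer patients are dispensed drug "according to the ACCP Guidelines of 6 weeks to 3 months" (Table 1, footnote 11), but must remain in the study "for the full 3 months to complete all remaining study visits, regardless of dalteparin treatment duration" (protocol 5.1). For those who stop before 3 months, "Anti-Xa and Anti-IIa plasma sampling will not be required after study medication discontinuation". Imaging is neither waived nor moved to the stop date.

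**The concern.** The label promises the state of the clot while the child is on dalteparin. The measurement is dated by the visit, not by the last dose. For a child who stopped as planned some weeks before Visit 7, the two come apart.

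Followed as written, clot extension first seen on that image is tabulated as progression on treatment, and resolution first seen on it is credited to treatment. The reported proportion then blends status at the end of treatment with status some time after it. The exact confidence interval does not reveal the blend. Results are split by age group only, not by cancer status or by whether the child was on drug at the image, so a reader could not separate the two.

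**Working it through.** **Does any rule tie the image to the last dose?**

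- A planned stop is not among the causes of early discontinuation in protocol 5.3. It is also not a removal from the study under 6.3.1.1, which would bring the Visit 7 assessments forward. So it triggers no image.
- SAP 2.2 speaks only of up to 90 days of treatment. It does not mention the shorter non-cancer course.
- SAP 5.3 says only that missing efficacy data are not imputed.
- The 30-day lag that defines the effective duration of treatment appears only under adverse events (SAP 3.4.1).

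No such rule was found.

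**How long is the gap?** The plan gives no figure to reproduce, so this is calendar arithmetic.

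Inputs: image on Days 75 to 104 (Table 1). As a check, protocol 5.3 gives 90 − 14 = 76 to 90 + 14 = 104, one day different at the lower end. Minimum non-cancer course: 6 weeks = 42 days.

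The start of the 6 weeks is ambiguous. Protocol 5.1 cites guidelines "which suggest a total duration of anticoagulation treatment of between 6 weeks and 3 months rather than shorter or longer durations", which reads as a count from the start of treatment, but the same sentence goes on to place the period after the PD Phase is completed. Protocol 7 has the PD Phase start on Day 2 or 3 and run to Day 14 at the latest. Both readings are shown.

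Days off drug = image day − last dosing day. Share = days off drug ÷ image day.

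| 6 weeks counted from | Last dosing day | Days off drug at image | Share of time to image |
|---|---|---|---|
| First dose | 42 | 75 − 42 = 33 to 104 − 42 = 62 | 33/75 = 44% to 62/104 = 60% |
| PD Phase ending Day 3 | 3 + 42 = 45 | 75 − 45 = 30 to 104 − 45 = 59 | 30/75 = 40% to 59/104 = 57% |
| PD Phase ending Day 14 | 14 + 42 = 56 | 75 − 56 = 19 to 104 − 56 = 48 | 19/75 = 25% to 48/104 = 46% |

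A PD Phase that ended on Day 2 would add one day to the second row.

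**Would the adverse-event lag rescue the label?** Adding 30 days to the last dosing day gives Day 72, Day 75 and Day 86. The first falls before the earliest Visit 7 image, the second only reaches it, and the third covers only part of the window.

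**And at 90 days?** For a course of 90 days from first dose, the latest image is 104 − 90 = 14 days after the last dose, and an image before Day 90 is on drug.

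**Effect on the proportions.** This cannot be computed, because the number of early stoppers is not given. Purely as an assumption: if 10% to 50% of 50 children were imaged off drug, and 10% to 30% of those changed category after stopping, 0.5 to 7.5 children (1 to 15 percentage points) would be involved.

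**The case against.** The case for leaving the plan alone has several parts.

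- **The words already restrict the endpoint.** A programmer could read the on-treatment wording as an instruction to drop off-drug images. But protocol 9.1.1 sends the measurement to the end-of-study image, and the SAP has no exclusion rule or window. The silence stands as part of the problem.
- **Many children are protected.** An earlier image showing resolution replaces the later one, suspected events are imaged when they occur, discretionary images are allowed, and removal from the study brings the final assessments forward where possible. This stands. A reader might infer that every non-cancer child's category describes a clot weeks after the last dose. The documents do not support that: the affected group is those who stop early with no such earlier image.
- **The 6-week gaps are the extreme.** This also stands. The permitted course runs to 3 months, where the gap shrinks towards zero, and nothing says how often the minimum is used.
- **Cancer patients are not a clean comparison.** A reader might infer that they are all imaged on or about their last dose. But under protocol 6.3.1 any child who stops drug early normally stays in follow-up, and a 90-day completer may be imaged up to about 14 days later. The blend follows cancer status only in part.
- **The endpoint carries little weight.** It is secondary, exploratory in its objective, uncontrolled and untested (SAP 2.1, 3.2 and 5.1). Treatment duration and cancer diagnosis are summarised elsewhere. This limits the importance, but a descriptive result still has to describe what was measured.

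**Conclusion.** The point holds in limited form. A non-cancer child who completes a planned course shorter than about 3 months, and who has no earlier image showing resolution or a new or progressive event, is classified from an off-drug image under an on-treatment label. Any other child who stops drug early but stays in follow-up, including one with cancer, is affected in the same way.

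For the 6-week minimum the image comes 19 to 59 days after the last dose when the course is counted from the end of the PD Phase (ending Day 3 to Day 14), or 33 to 62 days when counted from the first dose. These figures assume dosing for exactly 42 days from the chosen start and an image within Days 75 to 104.

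How far the reported proportions would shift is unknown. The problem falls mainly on the regression, no-change, progression and late-resolution categories. The primary PD endpoints are unaffected.

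**What to change.** In SAP 6.1.2.1 and protocol 12.3.5:

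1. Rename the result *status of the qualifying VTE at end of study (or at the earlier image showing resolution)*, and keep in it all PD-population children who have an image.
2. Report the days from last dose to image.
3. Show the overall result split by on or off dalteparin at the image, using a window that the sponsor prespecifies. The documents give no basis for a particular number of days.
4. Do not describe off-drug images as on-treatment. If an on-drug-only proportion is shown, make it supplementary and state that it selects towards cancer patients and longer-treated children.
5. Reconcile the two statements of when the non-cancer treatment period starts, since they move the off-drug interval by up to 14 days.

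Cost: wording and a derived interval, with no new images or visits. Dosing times go on the CRF (protocol 5.2). Images are kept with source records (9.1.6), but the documents do not show image date as a CRF field, so confirm that it is captured. The split will have small cells and wide intervals with a target of 50 children, which is why it is proposed for the overall result and not within age groups.

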## **6.2. Baseline and Other Summaries and Analyses**

### **6.2.1. Demography and Baseline Summaries**

The demographic characteristics will be summarized, overall and by each age group, within the safety population and the PD population. This will include age, gender, race, height, and baseline weight.

All baseline disease characteristics will be summarized overall and by each age group based within the safety population and the PD population. This will include diagnosis of cancer, previous history of VTE, risk factors for VTE and qualifying episodes of VTE.

### **6.2.2. Study Conduct and Subject Disposition**

Study conduct and subject disposition will be summarized within the safety population. The number of subjects screened, randomized, treated, completing and discontinuing from the study, as well as the number of subjects in each analysis set will be summarized overall and by each age group. For subjects who did not complete the study, the reasons for withdrawal from the study will be presented.

### **6.2.3. Study Treatment Exposure**

Duration of treatment will be summarized, overall and by each age group, within the safety population and the PD population.

#### **6.2.4. Concomitant Medications and Non-Drug Treatments**

All concomitant medications as well as non-drug treatments will be summarized overall and by each age group within the safety population.

### **6.3. Safety Endpoint Summaries and Analyses**

The safety summaries below will be performed within the safety population.

#### **6.3.1. Safety analysis**

- Proportion of subjects with major bleeding assessed by investigators during dalteparin treatment.

The count and proportion will be summarized overall and by each age group, along with the two-sided exact 95% CI.

- Relationship between major bleeding event and the Anti-Xa level during dalteparin treatment.

Logistic regression for major bleeding event assessed by investigators on anti-Xa level observed at the end of dose adjustment and other prognostic factors (eg, age, gender), will be performed. For each of the covariates, the odds ratio, and the corresponding 95% CI, will be displayed.

Subjects who experience at least one major bleeding event while on study will be counted as Yes.

- Proportion of subjects with minor bleeding events during dalteparin treatment.

The count and proportion will be summarized overall and by each age group, along with the two-sided exact 95% CI.

- Time to first major bleeding event during dalteparin treatment.

The time to first major bleeding event assess by investigators will be described by using the Kaplan-Meier method. In addition, the Cox Proportional Hazard Regression model will be employed to assess the hazard ratio of the event with prognostic factors.

See [Appendix 1.1](#) for a general description of censoring of time-to-event variables.

#### **6.3.2. Adverse Events**

All adverse events will be coded using the most current version of the MedDRA dictionary available at the time of database lock. Frequencies of adverse events will be presented by system organ class, preferred term, and severity level.

- All causality treatment emergent adverse events will be summarized overall and by each age group.

- Treatment related treatment emergent adverse events will be summarized overall and by each age group.
- Adverse events and serious adverse events will be listed by subjects for all age groups.
- Adverse events leading to discontinuation or temporary dose reduction will be presented.

Adverse events will be reported in accordance with the Pfizer Data Standards for safety reporting.

### **6.3.3. Laboratory Data**

Descriptive statistics will be summarized overall and by each age group as well as median change from baseline for laboratory parameters.

All laboratory data will be reported in accordance with Pfizer Data Standards for safety reporting.

### **6.3.4. Vital Signs and Physical Examination**

All vital sign and physical exam data will be reported in accordance with the Pfizer Data Standards for safety reporting.

## **7. INTERIM ANALYSES**

In August 2014, analyses for an interim report were performed by the previous study sponsor, Eisai Inc. on the data available at that time. The corresponding interim report was submitted to the FDA for review by Eisai Inc. These analyses did not contain any provisions for early stopping of the study.

## **9. APPENDICES**

### **Appendix 1. STATISTICAL METHODOLOGY DETAILS**

#### **Appendix 1.1. Time to Event**

For this analysis, time to event will be measured from the first dose of study medication in days. For subjects who have event, time to event is defined as:

$$T = \text{date of event} - \text{first treatment date} + 1$$

Subjects who do not have the event of interest will be censored at the latest date in the database. Time to event is defined as:

$$T = \text{latest date in the database} - \text{first treatment date} + 1$$

The latest date is expected to be the date of the End of Study visit.

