### **12.3.7. Some Statistical Considerations**

Censoring Criteria for Time to Events:

When there is no occurrence of the event, time to event will be censored to the date of last event assessment (last visit, death, or date of ET).

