### **3.2. Efficacy Endpoint(s)**

All efficacy endpoints are secondary endpoints.

- Proportion of subjects with objectively documented new or progressive symptomatic VTE during dalteparin treatment.
- Relationship between objectively documented new or progressive symptomatic VTE and the anti-Xa level during dalteparin treatment if data permits.
- The proportions of subjects with progression, regression, resolution or no change in the qualifying VTE during dalteparin treatment.
- Time to first episode of symptomatic recurrent VTE during dalteparin treatment.

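### The time-to-event analyses of recurrent VTE and major bleeding are defined as on-treatment, but the censoring rules run to the end of study, so off-drug time enters the risk set

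*SAP*

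**What the plan says.** **The endpoints.** SAP Section 3.2 lists "Time to first episode of symptomatic recurrent VTE during dalteparin treatment", and SAP 6.1.2.1 repeats it as "Time to event (first episode of recurrent VTE) during dalteparin treatment". SAP 3.4 and 6.3.1 attach the same on-treatment limit to time to first major bleed.

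**The censoring rules.** SAP Appendix 1.1 counts time from the first dose. For children without an event: "Subjects who do not have the event of interest will be censored at the latest date in the database". It adds: "The latest date is expected to be the date of the End of Study visit". Protocol 12.3.7 words it differently: "When there is no occurrence of the event, time to event will be censored to the date of last event assessment", which it explains as last visit, death or early termination. Neither rule mentions the last dose.

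**Treatment and follow-up.** Protocol 5.1 and 5.3 let non-cancer children be treated for 6 weeks to 3 months but keep them in the study for the full 3 months. Protocol 6.3.1 also keeps following children whose families ask to stop treatment. Protocol 5.3 puts End of Study at Day 90, plus or minus 14 days.

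**The regressions.** For the two logistic regressions on anti-Xa level, SAP 6.1.2.1 says "Subjects who experience at least one new or progressive VTE while on study will be counted as Yes" and SAP 6.3.1 says "Subjects who experience at least one major bleeding event while on study will be counted as Yes".

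**The only treatment window.** SAP 3.4.1 sets a 30-day lag for treatment-emergent adverse events. The VTE and bleeding analyses do not refer to it.

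**The concern.** An on-treatment Kaplan-Meier curve should hold a child at risk only while that child is on drug, or within a stated lag of it. Here a child who stops at 6 weeks stays in the denominator until End of Study. There are two ways to read the event side.

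- **Only on-drug events count.** Stopped children then remain at risk but cannot have an event, and the estimated risk is biased down.
- **Off-drug events count too.** The estimate is then not on-treatment. It may lie above, below or at the on-treatment value, depending on the off-drug hazard.

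The study has no control group (Protocol 5.2), so the absolute risk over time is what a reader takes from these curves. Planned early stopping applies only to non-cancer children, so off-drug time is also unevenly spread over baseline tumor type, which Protocol 12.3.5 and 12.3.6 give as an example Cox factor. Two analysts could follow the SAP and report different results.

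**Working it through.** The plan states no figure for this point, so there is nothing to reproduce. The first step uses the documents' own durations; the later steps are illustrations with assumed inputs.

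**1. Off-drug days for a non-cancer child who stops at 6 weeks**

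The earliest planned stop is Day 42 if 6 weeks run from the first dose, or Day 42 + 14 = Day 56 if they run from a PD Phase that ends on Day 14.

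| Stop | End of Study | Off-drug days | Share of follow-up | Days beyond a 30-day lag |
|---|---|---|---|---|
| Day 42 | Day 90 | 90 − 42 = 48 | 53% | 90 − 72 = 18 |
| Day 56 | Day 90 | 90 − 56 = 34 | 38% | 90 − 86 = 4 |
| Day 42 | Day 104 | 104 − 42 = 62 | 60% | 104 − 72 = 32 |
| Day 56 | Day 76 | 76 − 56 = 20 | 26% | 0 |

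A child treated up to End of Study contributes none.

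**2. Effect on the 90-day Kaplan-Meier estimate if only on-drug events count**

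Assumed: 90-day on-drug risk of 10%; constant hazard; a share q of 25% to 75% of all children stopping at day s = 42 or 56; all others treated to Day 90; no other losses.

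- Hazard: h = −ln(0.9)/90 = 0.0011707 per day.
- Estimate: 1 − [(1 − q) × 0.9 + q × exp(−h × s)].
- q = 0.75, s = 42: exp(−0.04917) = 0.9520, so 1 − (0.2250 + 0.7140) = 6.10%.
- q = 0.25, s = 56: exp(−0.06556) = 0.9365, so 1 − (0.6750 + 0.2341) = 9.09%.

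Censoring at the stop day would give 10% under these assumptions.

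**3. Sensitivity, still with only on-drug events counted**

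- Half as many children stopping (q = 0.125 to 0.375): 8.05% to 9.54%.
- Hazard three times higher in the first 30 days, rescaled to 10% at Day 90: 7.69% to 9.46%.
- 30 days after the last dose treated as on-treatment (s = 72 or 86, q = 0.25 to 0.75): 8.56% to 9.89%.

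**4. If off-drug events also count**

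Replace exp(−h × s) by exp(−h × s − r × h × (90 − s)), where r is the off-drug hazard relative to the on-drug hazard. With r = 1 the estimate stays at 10%. With r = 2 it is 10.88% (q = 0.25, s = 56) to 13.69% (q = 0.75, s = 42).

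**5. Scale**

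An observed 10% in 50 children is 5 events. The exact 95% interval (Clopper-Pearson) is 3.3% to 21.8%, wider than any shift above.

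**The case against.** **The regressions.** A reader might infer that all four analyses contradict their headings. The documents do not support that. In the heading "Relationship between major bleeding event and the Anti-Xa level during dalteparin treatment" the treatment phrase stands next to the anti-Xa level and can describe the level rather than the event. The corresponding objective (Protocol 4, SAP 2.1) carries no on-treatment limit, although the bleeding and symptomatic VTE objectives beside it do. Counting every event on study may be exactly what is intended. The regression window is therefore ambiguous, not clearly contradictory.

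**Off-drug events.** A reader might also infer that off-drug events are certainly counted, so that the risk could be overstated. The endpoint definitions limit the event to treatment, and the SAP calls its appendix a general description of censoring. Read together, they favor leaving off-drug events out. The risk-set problem remains, and so the downward bias is the main issue.

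**Importance.** The analyses are secondary and descriptive. SAP 5.1 states no hypotheses, even though SAP Section 6 names a two-sided 0.05 level for tests. The simple proportions with exact intervals also report absolute risk, and no study-window censoring rule applies to them. The size of the bias rests on assumptions. All of this stands and limits the weight of the point.

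**Choice of window.** A whole-study window is a legitimate choice and avoids informative censoring. Removing the on-treatment wording would end the mismatch. It would also leave the endpoint that the SAP defines without an analysis.

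**Conclusion.** The point holds for the two time-to-event analyses. Their definition is on-treatment, both censoring rules run past the last dose, and the design guarantees off-drug follow-up for any child who stops early and stays in the study. Off-drug time enters the risk set on either reading. On the more natural reading the Kaplan-Meier risk is biased down.

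From the documents' durations alone, a child stopping at Day 42 to 56 is off drug for 38% to 53% of a 90-day follow-up. The fall from 10% to 6.1%–9.1% is an illustration: the risk, the hazard shape and the share stopping are all assumed. It should not be read as a strict bound, because children may also stop on request before Day 42. It lies within sampling error at 50 subjects.

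For the two regressions the finding is only that the window is unclear. The primary pharmacodynamic endpoints are unaffected. This should be corrected before analysis, but it does not threaten the study's main conclusions.

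**What to change.** - **SAP Appendix 1.1.** For the two on-treatment time-to-event analyses, count events only up to the last dalteparin dose plus one prespecified lag. Censor event-free children at the earliest of that date, death or last assessment. State how this lag relates to the 30-day lag in SAP 3.4.1.
- **Supplement.** Report the whole-study analysis under its own label. It shows later events and helps the reader judge whether stopping was informative.
- **SAP 6.1.2.1 and 6.3.1.** For the regressions, either use the same window or keep the on-study count and label the results whole-study.
- **Protocol 12.3.7.** Align it at the next amendment, or record the difference in the SAP. A separate amendment would need approval and notice to the ethics committee (Protocol 16.7), which this point alone hardly justifies.

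The cost is SAP wording and a small extra output. No new data are needed: dosing times go on the CRF (Protocol 5.2), and the treatment-duration summaries (Protocol 12.3.6, SAP 6.2.3) already need the last-dose date. The drawbacks are slightly less follow-up in the main analysis and censoring that may be informative.
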